9.3.5 Adverse Event Reporting

We will be adopting the following reporting procedures:

What	event	is	When	is	event	Ву	whom	is	event	То	whom	is	event
reported			reported			rep	orted			rep	orted		

Fatal or life-threatening unexpected, suspected serious adverse reactions	Within 24 hours of initial receipt of information	Investigator	 Local/internal IRB Sponsor
Non-fatal, non-life-threatening unexpected, suspected serious adverse reactions	Within 48 hours of initial receipt of information	Research Personnel	 Local/internal IRB Sponsor
Unanticipated adverse device effects	Within 10 working days of investigator first learning of effect	Investigator	 Local/internal IRB Sponsor
Unanticipated Problem that is not an SAE Within 7 days of the investigator becoming aware of the problem		Investigator	 Local/internal IRB Sponsor

9.3.6 REPORTING OF PREGNANCY

Women of child-bearing potential are asked if they are pregnant or plan to become pregnant before the stimulation session. Furthermore, they are asked to use an appropriate method of birth control for the duration of trial participation. Importantly, there is no evidence that suggests tACS would interfere with pregnancy [20]. However, should a participant become pregnant during the five days of stimulation, their participation stimulation will be immediately terminated and the participant will be followed until giving birth.

9.4 UNANTICIPATED PROBLEMS

9.4.1 DEFINITION OF UNANTICIPATED PROBLEMS (UP)

The Office for Human Research Protections (OHRP) considers unanticipated problems involving risks to participants or others to include, in general, any incident, experience, or outcome that meets all of the following criteria:

- Unexpected in terms of nature, severity, or frequency given (a) the research procedures that are described in the protocol-related documents, such as the Institutional Review Board (IRB)-approved research protocol and informed consent document; and (b) the characteristics of the participant population being studied;
- Related or possibly related to participation in the research ("possibly related" means there is a reasonable possibility that the incident, experience, or outcome may have been caused by the procedures involved in the research); and
- Suggests that the research places participants or others at a greater risk of harm (including physical, psychological, economic, or social harm) than was previously known or recognized.

9.4.2 UNANTICIPATED PROBLEM REPORTING

If a UE occurs, the IRB and the sponsor will be notified, and the study will be adjusted as needed to protect the health and safety of the participants. Depending on the nature of the UE, the research protocol, inclusion/exclusion criteria, and informed consent will be changed to reflect the possibility of this event reoccurring. During this time, no new participants will be recruited and the research procedures for currently enrolled participants will be stopped. Each UE will be recorded and reported throughout the study.

9.4.3 REPORTING UNANTICIPATED PROBLEMS TO PARTICIPANTS

Any new information gained during the study that may affect a participant's willingness to continue in the study will be reported to all currently enrolled participants.

10. STATISTICAL CONSIDERATIONS

10.1 STATISTICAL HYPOTHESES

Primary Efficacy hypothesis:

- Null: There is no difference in depression severity measured by the HDRS-17 between FU2 and Day 1.
- Alternate: There is a difference in depression severity measured by the HDRS-17 between FU2 and Day 1.

10.2 SAMPLE SIZE DETERMINATION

A recently concluded pilot clinical trial compared the effects of 10 Hz tACS (therapeutic frequency) against 40 Hz tACS (control frequency). A total of 32 participants enrolled, 30 completed the 5-day intervention, and 26 completed both a 2 and a 4-week follow-up session. With approximately 9 participants in each group, a significant reduction was found in alpha oscillation power on the fifth day of stimulation (p < 0.05) [6], which is the presumed mechanism of action of closed-loop tACS. Therefore, with a total of 35 participants we anticipate we will find a significant difference. Further support for this sample size from this previous study derives from a Cohen's dz = 1.58 for change in HDRS-17 score from baseline to the 2-week follow up. For an alpha = 0.05 (two-sided) and a power of 0.95, the required sample size is N=8 based on calculation by G*power 3.1.9.7. The plot below shows how power changes as a function of effect size for a sample size of N=10. As can be seen, the current design is well-powered for the expected effect size for clinical outcomes, and adequately powered (i.e. 80%) for effects as low as dz = 1 for any given outcome measure.

However, the expected effects of stimulation for secondary outcome measures at FU2 are currently unclear, and self-report measures tend to have more variability and thus reduced effect sizes when compared to clinician-administered measures like the HDRS-17. Moreover, studies looking to replicate prior findings are known to require larger sample sizes compared to the original study. To that end we conducted design sensitivity analyses. We reason that a target of N = 28 for a complete dataset allows for a sound evaluation of any given effect down to dz = 0.55 which is traditionally considered in psychological research to be a medium-sized effect for two-tailed α = 0.05 at 80% power.

In the previous trial, 80% of the participants completed all study sessions. We are thus anticipating consenting around 35 people to reach the goal of 28 people for analysis. The power calculation above demonstrates what statistical conclusions will be feasible with a sample size of 28 completers.

10.3 POPULATIONS FOR ANALYSES

Every effort will be made to ensure all enrolled participants complete all study sessions as described in this protocol.

As previously stated in **Section 7 Study Intervention Discontinuation and Participant Discontinuation/Withdrawal**, enrolled participants who do not complete the full intervention will be replaced. Therefore, with this population for analysis plan, we anticipate having data from 35 participants that are eligible for analysis.

10.4 STATISTICAL ANALYSES

10.4.1 GENERAL APPROACH

All testing described below assumes a significance threshold of alpha = 0.05. Continuous data will be described using means and standard deviations, while categorical data will be described using counts/percentages.

There will be no pre-specified covariates described in this protocol. Data will be assessed for normality and, if deemed necessary, corrective procedures will be applied (e.g., log normalization).

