4. OBJECTIVES AND OUTCOME MEASURES

OBJECTIVES	ENDPOINTS	JUSTIFICATION FOR ENDPOINTS
Primary		
To determine the effect of CLtACS on depression symptom severity	Change in HDRS-17 between two-week follow-up (FU2) and Day 1 (D1)	The HDRS-17 is the standard clinician-administered instrument to measure change in symptom severity in people with MDD
Secondary		
To determine the effect of CLtACS on depression symptom severity	Change in HDRS-17 between D5 and Baseline/ D1	The HDRS-17 is the standard clinician-administered instrument to measure change in symptom severity in people with MDD.
To determine the remission and response rate of CLtACS Response is defined as >= 50% reduction rate in HDRS-17 score relative to D1 Remission is defined as	Number of response/remission rates at D5 and FU2	Remission and response rates provide additional insights into the efficacy of a treatment.

OBJECTIVES	ENDPOINTS	JUSTIFICATION FOR ENDPOINTS
To determine time-course of symptom change	Change in Quick Inventory of Depressive Symptomatology (QIDS) at D5, FU1, FU2	Battery of self-report measures of mood and related constructs at the 7-day follow up (digitally
	Change in Altman Self-Rating Mania Scale (ASRM) at D5, FU1, FU2	delivered) provide additional insights into the symptom changes in between the
	Change in Snaith-Hamilton Pleasure Scale (SHAPS) at D5, FU1, FU2	clinician administered assessment on Day 5 and at FU2.
	Change in Depression Anxiety and Stress Scale (DASS-42) at D5, FU1, FU2	
	Change in State-Train Anxiety Inventory (STAI) at D5, FU1, FU2	
	Change in Quality of Life Enjoyment and Satisfaction Questionnaire, short form (Q-LES-Q-SE) at D5_EU1_EU2	
	Change in Clinical Global Impression Scale (CGI) at D5, FU2	
Exploratory		
Feasibility	Fraction of participants who complete the 5-day course of stimulation	Since the primary outcome is determined from the subgroup of people who have completed stimulation, examining the fraction of people who complete the stimulation paradigm is important to minimize bias in case of people discontinuing study participation due to lack of perceived efficacy or symptoms worsening.
To determine the effect of CLtACS on endogenous EEG alpha oscillations	Change in HD-EEG alpha oscillation power at D1 pre-stimulation, D1 post-stimulation, and FU2	The inclusion of EEG endpoints provides insights into the network-level mechanisms underlying the treatment effects.

OBJECTIVES	ENDPOINTS	JUSTIFICATION FOR ENDPOINTS				

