7.2 MEASURES TO MINIMIZE BIAS: RANDOMIZATION AND BLINDING

Randomization

There is no randomization since this is an open-label pilot study.

Blinding

There is no blinding since this is an open-label pilot study.

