10.4.2 ANALYSIS OF THE PRIMARY EFFICACY ENDPOINT (DEPRESSION SEVERITY)

We will perform a paired t-test to establish the statistical significance of the change in depression symptom severity (two-sided, alpha = 0.05). Additional, strictly exploratory analyses will take into account baseline scores as covariates (e.g., degree of treatment resistance measured by the Maudsley scale).

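### Does the open-ended normality clause leave the scale of the primary HDRS-17 test to be chosen after the data are seen?

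*Combined protocol and SAP*

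**What the plan says.** Section 10.4.1 (General Approach) opens with the significance level: "All testing described below assumes a significance threshold of alpha = 0.05". Its second paragraph, after ruling out pre-specified covariates, adds the normality clause: "Data will be assessed for normality and, if deemed necessary, corrective procedures will be applied (e.g., log normalization"). The clause gives no test, threshold, timing or list of variables, and log is its only example.

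The text specific to the primary analysis is consistent:

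- Section 4, endpoint: "Change in HDRS-17 between two-week follow-up (FU2) and Day 1 (D1").
- Section 10.1, null hypothesis: "Null: There is no difference in depression severity measured by the HDRS-17 between FU2 and Day 1". The alternative is: "There is a difference in depression severity measured by the HDRS-17 between FU2 and Day 1".
- Section 10.2, planning effect: "dz = 1.58 for change in HDRS-17 score from baseline to the 2-week follow up".
- Section 10.4.2, test: "We will perform a paired t-test to establish the statistical significance of the change in depression symptom severity (two-sided, alpha = 0.05").

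None of these mentions a transformed score. None says in so many words that the scores stay untransformed.

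**The concern.** The normality clause sits in the general section and exempts no endpoint, so it can be read as reaching the primary test. Whoever judges a correction necessary would do so with the data in hand, and Section 7.2 confirms that "There is no blinding since this is an open-label pilot study". If the scale could be settled after seeing which version gives the smaller p-value, the 5% level would not be protected.

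The example also fits this endpoint badly. A signed change has no logarithm, so the D1 and FU2 scores would have to be logged separately. The test would then address a ratio of geometric means and not the stated difference. Falls from 24 to 16 and from 12 to 4 are both −8 on the raw scale, but ln(16/24) = −0.41 and ln(4/12) = −1.10. A follow-up score of 0 would also need an offset that the plan does not state.

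**Working it through.** **1. The plan's own figures.** Power of a two-sided paired t-test comes from the noncentral t distribution with df = n − 1 and noncentrality dz × √n.

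- dz = 1.58: power is 0.933 at n = 7. At n = 8 the noncentrality is 1.58 × √8 = 4.47 and power is 0.967. The stated N = 8 for 95% power is reproduced.
- dz = 1, n = 10: power 0.803, against the stated 80%.
- dz = 0.55, n = 28: noncentrality 0.55 × √28 = 2.91, power 0.801, against the stated 80%.
- Consented participants: 28 / 0.80 = 35, as stated.

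The planning effect is defined on change in score, so these figures already presuppose a raw-scale test. Writing the scale down would alter none of them.

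**2. What an open scale could do.** The documents give no means, SDs or correlation, so these inputs are assumptions: n = 28, D1 mean 17 and SD 4, FU2 SD from 4 to 7, within-person correlation 0.5, integer scores limited to 0–52, and log(score + 1) where log is used. The entry limit (HDRS-17 above 8) is from Section 6.1. True means are set equal, so nominal error is 5%. There were 40,000 simulated trials per row.

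| FU2 SD | Raw | Log if Shapiro-Wilk on the change fails | Log if the change or either visit's scores fail | Log always | More favourable scale picked |
|---|---|---|---|---|---|
| 4 | 5.2% | 5.2% | 5.2% | 5.2% | 6.0% |
| 5 | 5.1% | 5.2% | 5.2% | 5.6% | 6.8% |
| 6 | 5.0% | 5.2% | 5.3% | 6.6% | 8.2% |
| 7 | 5.1% | 5.3% | 5.7% | 8.5% | 10.3% |

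Varying the correlation from 0.3 to 0.7 leaves the rule on the change at 4.9–5.4%.

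The clause makes any correction conditional on a normality assessment. The third and fourth columns therefore model it, and the last two do not. Part of the excess under log always is not false positives in the usual sense: when the arithmetic means are equal but FU2 is more variable, the logged means do differ.

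**3. Skewed follow-up scores.** With right-skewed (gamma) FU2 scores and SD 4, 5, 6, 7, error is:

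- raw: 5.0, 5.2, 5.1, 5.2%
- Shapiro-Wilk rule on the change: 5.1, 5.5, 5.7, 6.6%
- log always: 5.1, 6.1, 7.6, 10.5%

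The raw test keeps 77–79% power at dz = 0.55, so skewness gives little reason to leave it.

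**4. Does the conclusion change?** Under the Shapiro-Wilk rule with normal scores, the verdict differs from the raw test in 0.4–0.7% of trials at dz = 0.55. With the most skewed and most variable FU2 scores it differs in up to 8%. At dz = 1.58 it never differs. Compared without any rule, raw and log disagree in 4, 7, 9 and 12% of trials at dz = 0.55 (normal scores, FU2 SD 4 to 7) and in under 0.1% at dz = 1.58.

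**The case for a change.** The strongest case for a change is structural. The primary t-test is the only hypothesis test that Section 10.4 specifies: response and remission are not tested, and safety is descriptive. If the clause does not reach the primary test, it has no named test to govern. The trial is also sized for effects down to dz = 0.55, where the choice of scale can matter, and one sentence would close the gap.

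Part of this stands. The clause exempts nothing, and the discretion is undefined. But the phrase about all testing belongs to the sentence on the significance level. The normality sentence concerns data in general, which here include EEG alpha power and several rating scales listed in Section 4. Log is offered only as an example, and its drawbacks for HDRS-17 would discourage its use. If FU2 has mean 8 and SD 4 to 6 (assumed), 58–95% of samples of 28 contain at least one zero, so an analyst would have to invent an offset in plain view.

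The open-label point adds little. A single arm has no allocation to conceal, and any normality check needs the data. The 8% rate of changed verdicts at dz = 0.55 is real under its assumptions, but it needs strong skewness together with an SD rising from 4 to 7.

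**Conclusion.** The observation is accurate, but it does not call for a change. The plan leaves a detail unstated that its endpoint, hypotheses, effect size and named test already settle: a paired t-test on the raw HDRS-17 change. A competent analyst would run that test and treat any transformed version as supplementary. Stating the scale would be tidier, but it would change no sample size, no power figure and no expected analysis.

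If the clause were applied mechanically to the change, error would stay close to 5% with normal scores and reach 6.6% in the worst skewed case examined. The conclusion at the planning effect would not change. Inflation to about 10% requires logging regardless of the check with strongly skewed follow-up scores, or selecting the scale by its p-value, and the plan proposes neither. All the simulated figures depend on assumed means, SDs, correlation and distribution shapes, because the documents give none.

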10.4.2 ANALYSIS OF THE PRIMARY EFFICACY ENDPOINT (DEPRESSION SEVERITY)

We will perform a paired t-test to establish the statistical significance of the change in depression symptom severity (two-sided, alpha = 0.05). Additional, strictly exploratory analyses will take into account baseline scores as covariates (e.g., degree of treatment resistance measured by the Maudsley scale).

10.4.3 ANALYSIS OF THE SECONDARY ENDPOINT (RESPONSE AND REMISSION RATE, FEASIBILITY)

We will compute the response and remission rates for the sample. There is no statistical testing applicable for this outcome since there are no groups to compare.

We will compute the fraction of participants who complete stimulation by dividing the number of people who received 5-days of stimulation by the total number of participants who received any amount of stimulation.

As applicable, 95% confidence intervals will be computed to describe precision of the estimate.

10.4.4 SAFETY ANALYSES

As discussed in *Section 8.2, Safety and Other Assessments* safety will be assessed with the C-SSRS, an adverse effects questionnaire, and the Altman Self-Rating Mania Scale (ASRM).

The C-SSRS will be used to assess suicide risk. If a participant's responses have an elevated risk, the participant will be contacted, and an acute assessment will be completed if deemed necessary by Dr.

[name] or [name] (as described above). Any verified increases in suicidal ideation will be described in counts/percentages. The C-SSRS is administered at the screening visit and at the 14-day follow up.

The stimulation questionnaire will be administered at D1-D5 after stimulation. This questionnaire solicits ratings of 11 possible sensory experiences ("flickering light") and adverse effects ("scalp pain") associated with electrical stimulation, on a scale of 0 (absent), 1 (low), 2(medium), and 3 (high). Intensity of sensory experiences and adverse effects will be described with mean and standard deviation.

The Altman Self-Rating Mania Scale (ASRM) will be used to assess any development of mania over the course of treatment. A ASRM score of greater than 6 indicates the possible development of a manic episode. Any participant who scores greater than 6 on the ASRM will be assessed by [name] or [name]. Any verified manic episode will be described in counts/percentages.

The Adverse Events Structured Interview will be administered by research personnel at D5 and whenever a participant spontaneously reports a potential AE during trial participation. This interview solicits open-ended descriptions of 13 possible adverse effects a participant may experience in any clinical trial as well as one question of 'any other experiences'. Responses will be reviewed by the clinician and rated as described in **Section 8.3.** Severity per adverse effect will be described with mean and standard deviation.

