Risk of Injury and Discomfort: The side effects of tACS are mild and transient; in fact, low intensity transcranial current stimulation, such as tACS, has been used for several years without any report of serious side effects [12]. Furthermore, this stimulation mode has nothing to do with electroconvulsive therapy that applies many orders of magnitude higher stimulation current. Rather, transcranial current stimulation is so weak that it does not cause super-threshold activation of neurons [13]. However, tACS does have some mild side effects, such as transient mild tingling, burning, or itching under the electrode sites. [6]. To monitor these mild side effects, we will be administering a stimulation questionnaire after each stimulation session to determine whether these effects were experienced and at what intensity. Research personnel are present during the full experiment.

Patients with MDD have an about 20 times higher rate of suicide than average. We have no evidence that our treatment paradigms will in any way increase this likelihood. Rather, active engagement in a clinical trial may offer hope and structure to the participants. Regardless, participants with high suicide risk (intent or plan) will not be included in this study. If an enrolled participant shows signs of suicide risks that were not apparent during enrollment, a referral to UNC Psychiatry will be made. [name], Co-I, will facilitate this process.

We will be using the Columbia Suicide Severity Rating Scale (C-SSRS, triage form) [14] to determine intent for suicide during D1. Inclusion criteria state that the participant must be low suicide risk and that

potential participants with an above "low risk" designation will not be eligible for the study. In the event that suicide risk increases during participation in the study, the participant will be asked to stop the study. The participant will be provided with a referral to UNC Department of Psychiatry, and their mental health care or family medical doctor will be contacted.

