9.2 SAFETY AND OTHER ASSESSMENTS

9.2.1 SUICIDAL IDEATIONS AND SUICIDAL BEHAVIOR

Only participants deemed at low suicide risk based on the C-SSRS (ideation allowed, however intent, plan or attempt excluded) are enrolled in this study. The C-SSRS [14] will be administered by trained research personnel at screening and the follow-up session to thoroughly assess suicide risk. In addition, the answers to suicide-related questions on the HRDS-17 and on the QIDS will be monitored. Based on these sources of information, clinical personnel will decide if an acute assessment is required. Acute assessment may include facilitating contact of the participant with their psychiatrist or primary care physician to establish a plan for safety, continued care, and follow-up. If the participant does not have an established provider, [name] or [name] will assist in establishing a care plan. If at any point during the assessment, the participant is deemed an imminent risk of harm to self or others, study personnel will enlist the aid of security at the facility or first responders to ensure that the participant is safely escorted to the Emergency Department for further care. [name] and/or [name] will decide if participation should be stopped after the acute assessment. If the participant is hospitalized, their participation will end.

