11.1.6 SAFETY OVERSIGHT

Safety oversight will be under the direction of the Principal Investigator [name]. He will review all adverse events timely and serious adverse events and changes in the suicidality and mania ratings as fast as possible. Based on his review, continuation of participant's participation is decided. All SAE or unanticipated AE will be reported to the local IRB and the sponsor.

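### Sections 3.3.1, 8.1 and 9.2.1 give incompatible responses to increased suicide risk in an enrolled participant

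*Combined protocol and SAP*

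**What the plan says.** Section 3.3.1 (Known Potential Risks) covers the matter twice. One paragraph gives a referral only: "If an enrolled participant shows signs of suicide risks that were not apparent during enrollment, a referral to UNC Psychiatry will be made". A later paragraph goes further: "In the event that suicide risk increases during participation in the study, the participant will be asked to stop the study". It continues: "The participant will be provided with a referral to UNC Department of Psychiatry, and their mental health care or family medical doctor will be contacted". Neither paragraph mentions an assessment, a threshold or a clinical decision.

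Section 8.1 (Discontinuation of Study Intervention) ends stimulation when an acute assessment finds that suicidal risk has significantly increased. It says that leaving stimulation is not leaving the study, and it invites the participant to the FU1 questionnaires and the FU2 assessment.

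Section 9.2.1 (Suicidal Ideations and Suicidal Behavior) draws on the C-SSRS and the suicide items of the HDRS-17 and QIDS: "Based on these sources of information, clinical personnel will decide if an acute assessment is required". Helping the participant reach their psychiatrist or primary care physician is something the assessment may include, and stopping is decided after it. Some steps are firm: escort to the Emergency Department for imminent risk, end of participation on hospitalization, and help with a care plan for someone without a provider.

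Section 10.4.4 (Safety Analyses) says that when C-SSRS responses show elevated risk, "the participant will be contacted, and an acute assessment will be completed if deemed necessary", followed by a reference back to an earlier description.

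Section 11.1.6 (Safety Oversight) has the Principal Investigator review adverse events and changes in suicidality and mania ratings, and continuation is decided on that review.

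**The concern.** Section 3.3.1 is part of the risk description on which the risk/benefit conclusion in 3.3.3 rests. A reader of 3.3.1 would expect a referral, contact with the participant's doctor and a request to stop whenever risk increases. Staff working from 9.2.1 could comply without a referral or clinician contact, and with the participant continuing.

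There is also a data consequence. The primary endpoint is the change in HDRS-17 from D1 to FU2. Under 3.3.1 a participant whose risk rises before FU2 is asked to leave. Under 8.1 a participant taken off stimulation is still invited to FU2. The participants concerned may be those who are getting worse, so the section followed can decide whether their FU2 score is collected.

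**Working it through.** This is a comparison of text; no formula is involved. The responses side by side:

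| Section | Trigger | Acute assessment | Psychiatry referral | Contact with own clinician | Stopping |
|---|---|---|---|---|---|
| 3.3.1, first paragraph on suicide | Signs of risk not seen at enrollment | Not stated | Will be made | Not stated | Not stated |
| 3.3.1, second paragraph on suicide | Risk increases | Not stated | Will be given | Will be made | Asked to stop the study |
| 8.1 | Significantly increased risk | Needed to establish the trigger | Not stated | Not stated | Stimulation only; FU1 and FU2 offered |
| 9.2.1 | C-SSRS, HDRS-17 and QIDS items | Clinical judgement | Not stated as a step | May be part of the assessment | Decided after assessment; automatic on hospitalization |
| 10.4.4 | Elevated C-SSRS responses | If judged necessary, with a reference back | Not stated | Not stated | Not stated |
| 11.1.6 | General safety review | Not stated | Not stated | Not stated | Decided on review |

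Two cases show that the rows cannot all be followed.

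1. *Risk rises during the stimulation week.* Under the second 3.3.1 paragraph the participant is asked to leave the study, is referred and has their doctor contacted. Under 8.1, if an acute assessment finds the increase significant, stimulation ends and the participant is invited to FU1 and FU2. Under 9.2.1 there may be no assessment, and if there is one, stopping is still to be decided.
2. *Risk rises after D5 and before FU2, for example on the QIDS at FU1.* Stimulation is over, so 8.1 has nothing to stop. Section 3.3.1 still asks the participant to leave; 9.2.1 leaves this to a decision after assessment. Section 8.2 says that a participant who leaves before the two-week follow-up is not replaced, so an FU2 score lost this way is not made up.

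Two limits apply to the data consequence. Section 10.4.4 places the C-SSRS at screening and at the 14-day follow-up, so the signals before FU2 come mainly from the HDRS-17 and QIDS suicide items at D5 and the QIDS at FU1. Also, the feasibility row in Section 4 says the primary outcome comes from people who completed stimulation. In case 1 the FU2 score may therefore be collected yet not used in the primary analysis. In case 2 it would be used.

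For scale, 10.2 plans 35 consented with 80% completing: 35 × 0.80 = 28. One participant who leaves before FU2 is 1/28 = 3.6% of that target.

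**The case against.** The strongest reply is that the sections describe stages: a questionnaire signal, clinical review, an acute assessment if needed, a finding of increased risk, then stopping. Section 8.1 requires an assessment before stopping, 10.4.4 reports only verified increases, and the triggers are worded differently. This is a sensible reading of 8.1, 9.2.1 and 10.4.4 together. It does not bring in 3.3.1, which states no confirmation step and whose first paragraph on suicide acts on signs alone. Nor does it settle whether the participant leaves the study or only stimulation.

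A second reply is that 10.4.4 is an analysis section that summarizes 9.2.1. That stands. A reader might infer from 10.4.4 alone that a telephone call is enough, but its reference back appears to bring in 9.2.1 with its firm emergency steps. The conflict lies between 3.3.1 and Sections 8.1 and 9.2.1.

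Other stronger readings also fail:

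- 3.3.1 does not make an acute assessment mandatory, since it mentions none for an enrolled participant. Sections 9.2.1 and 10.4.4 agree that assessment is a judgement.
- 3.3.1 does not remove the participant. It states a request to stop, with no condition attached.
- The reported count of verified increases is not shown to depend on the section followed, because 3.3.1 has no verification step.
- 11.1.6 is general oversight and weak evidence of conflict. Names are removed from the other sections, so it cannot be told whether the deciding persons differ.

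**Conclusion.** The contradiction is real. For increased suicide risk in an enrolled participant, 3.3.1 states referral, doctor contact and a request to stop the study without discretion. Section 9.2.1 makes stopping a decision and provider contact a possibility. Section 8.1 sets a higher threshold and stops stimulation only. The consequence for the individual is whether two protective steps happen and whether they are asked to leave or stay in follow-up to FU2.

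The number of participants affected is unknown, because the documents give no rate of raised risk. A reader might infer a material bias in the primary analysis; the documents do not support a size for it. The conclusion assumes that 10.4.4 refers back to 9.2.1 and that risk increase in 3.3.1 carries its plain meaning. It takes no view on which clinical rule is right. The point should be corrected because these are conflicting safety rules, not missing detail.

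**What to change.** Reconcile 3.3.1 (both paragraphs), 8.1, 9.2.1 and 10.4.4 into one pathway, written once and cited from the other places. For each of five steps (acute assessment, referral, contact with the participant's clinician, stopping stimulation, stopping the study), state the trigger, whether the step is required or a clinical judgement, and which role decides. Say also whether someone who stops stimulation or the study for this reason is still invited to FU2.

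Check 11.1.6 against the result, but keep its general oversight of adverse events and mania. Check that the consent form describes the same pathway. The investigators choose the content.

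The cost is an amendment to wording with IRB review and the consent-form check. It needs no extra visits or participants and no change to the statistical analysis.
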